#### **7.4.6. Total Number of EDs per Patient**

The total number of EDs on rFIXFc for each patient will be summarized. This analysis is described in Section [6.6.1.1](#).

	Statistical Analysis Plan	Final v1.0
---	----------------------------------	-------------------

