6.2.2. Secondary Endpoints

The secondary endpoints of the study are as follows:

- the annualized number of bleeding episodes (spontaneous and traumatic) per subject
- the annualized number of spontaneous joint bleeding episodes per subject
- assessments of response to treatment with rFIXFc for bleeding episodes, using the 4-point bleeding response scale (Investigator assessment for bleeding episodes treated in the clinic; parent or caregiver assessment for all other bleeding episodes)
- the total number of EDs per subject per year
- total annualized rFIXFc consumption per subject for the prevention and treatment of bleeding episodes

CONFIDENTIAL

The information contained herein may not be used, disclosed, or published without the written consent of Bioverativ Therapeutics Inc

- the number of injections and dose per injection of rFIXFc required to resolve a bleeding episode
- rFIXFc incremental recovery

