16.5.2.3. Other Safety Parameters

Clinical laboratory values will be summarized for change from baseline, shifts, and potentially clinically significant abnormalities. Threshold levels for potentially clinically significant laboratory abnormalities will be provided in the SAP. Listings of abnormal laboratory test results will be provided.

Vital signs will be summarized by the number and percentage of subjects with abnormalities. Abnormal values will be defined in the SAP. A listing of abnormal vital signs will be provided.

Duration of exposure and the total number of EDs to rFIXFc per subject will be summarized overall based on the Safety Analysis Set; selected analyses may be based on the Supporting Analysis Set.

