#### **2.2.2. Secondary Endpoints**

The secondary endpoints of the study are as follows:

- The annualized number of bleeding episodes per patient (annualized bleeding rate [ABR]).
- The annualized number of spontaneous joint bleeding episodes per patient.
- Assessments of response to treatment with rFIXFc for bleeding episodes, using the 4-point bleeding response scale (Investigator assessment for bleeding episodes treated in the clinic; parent or caregiver assessment for all other bleeding episodes).
- Total number of EDs per patient per year.
- Total annualized rFIXFc consumption per patient for the prevention and treatment of bleeding episodes.
- The number of injections and dose per injection of rFIXFc required to resolve a bleeding episode.
- rFIXFc incremental recovery (IR).

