## End-of-Treatment Visit

End of Treatment (EOT) for individual patients is defined as follows:

- A patient who completes at least 50 EDs of rFIXFc and is not on an ITI regimen, is considered to have completed treatment.
- A patient undergoing ITI with rFIXFc is considered to have completed treatment if either of the following occurs:
  - The patient achieves successful immune tolerance as defined in protocol [Section 10.2.6](#).
  - The patient completes 24 months on an ITI regimen without achieving successful immune tolerance.
- Individual patients may also have to end treatment because one of the following has occurred:
  - The patient meets the criteria for early withdrawal.
  - Study stopping rules are met.
  - EOS is reached.

Upon ending treatment for any of the reasons described above, the subject will return to the site for the ET/EOS visit.

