### 6.6.1. Exposure

#### 6.6.1.1. Number of Injections and Exposure Days to rFIXFc

For any patient, the total number of days of exposure to rFIXFc will be accumulated from the time of their first on-study injection of rFIXFc. An ED is a 24-hour period in which one or more rFIXFc injections are given. The 24-hour window starts from the first injection on study and then for subsequent injections, it starts from an injection taken after/outside of a previously identified ED.

The total number of EDs on rFIXFc for each patient will be summarized categorically (<5, 5-<10, 10-<20, 20-<50, 50-<75, 75-<100 and >=100) and with descriptive statistics for the Safety Analysis Set.

The total number of injections per patient will be summarized overall and by reason for injection (prophylactic regimen, ITI regimen, spontaneous bleed, traumatic bleed, follow-up injection, surgical and other) using descriptive statistics for the Safety Analysis Set.

These tables will be presented by treatment regimen as described in Section 5.1.1.

The total number of injections and EDs will also be summarized by EPD entry compliance (see Section 6.6.2.3), <80% and >=80%, where >=80% is considered compliant.

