## 10. CHANGES TO PLANNED ANALYSIS

This SAP is based on Version 3 of the approved study protocol dated 06 August 2018. The major differences in the analysis described in this SAP compared to the protocol are:

- The Full Analysis Set consists of all patients who received at least 1 dose of rFIXFc and were enrolled.
- The protocol mentioned selected analyses may be performed based on a Supporting Analysis Set as appropriate. This analysis set is not defined in the SAP, and all analyses will be based on the analysis populations defined in Section 4.
- The health outcomes questionnaire used in the study is not as specified in the protocol. The analysis described refers to that which was actually used and this can be found in [Appendix A](#).

	Statistical Analysis Plan	Final v1.0
---	----------------------------------	-------------------

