## 12. LIST OF TABLES, LISTINGS, AND FIGURES

### List of tables

Background/Demography
Summary of disposition by treatment regimen
Summary of enrollment by country and site by treatment regimen
Summary of patients attending key study visits
Summary of patients attending key ITI study visits
Summary of demographics and baseline characteristics by treatment regimen
Summary of medical and surgical history by treatment regimen
Summary of hemophilia history by treatment regimen
Summary of bleeding history in the 3 months prior to study entry by treatment regimen
Summary of risk factors by inhibitor subgroup
Summary of physical examination at screening by treatment regimen
Summary of prior medications and procedures by treatment regimen
Summary of concomitant medications and procedures by treatment regimen
Summary of major protocol deviations by treatment regimen
Exposure/Dosing
Summary of injections and days of exposure to rFIXFc by treatment regimen
Summary of injections and days of exposure to rFIXFc by EPD entry compliance by treatment regimen
Summary of duration of dosing with rFIXFc by treatment regimen
Summary of duration of dosing with rFIXFc by EPD entry compliance by treatment regimen
Summary of prophylactic dose IU/kg
Summary of ITI dose IU/kg
Summary of prophylactic dosing interval
Summary of ITI dosing interval
Summary of annualized rFIXFc consumption (IU/kg) by treatment regimen
Summary of last prescribed prophylactic dose and dosing frequency
Summary of compliance for the treatment of bleeding episodes by treatment regimen
Summary of prophylactic and ITI dose compliance
Summary of prophylactic and ITI dosing interval compliance
Summary of prophylactic and ITI compliance
Summary of EPD entry compliance by treatment regimen
Efficacy
Summary of bleeding episodes by treatment regimen
Summary of annualized bleeding rates by treatment regimen
Summary of annualized bleeding rate by type of bleed and treatment regimen
Summary of annualized bleeding rate by location of bleed and treatment regimen
Summary of annualized bleeding rate by location, type of bleed and treatment regimen
Summary of annualized bleeding rate by history of bleeding (estimated frequency of bleeds in prior 3 months) by treatment regimen

	Statistical Analysis Plan	Final v1.0
---	----------------------------------	-------------------

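### The secondary endpoint of exposure days per patient per year is analysed only as a total: no formula or listed table annualizes it.

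*SAP*

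**What the plan says.** Protocol 6.2.2 names as a secondary endpoint "the total number of EDs per subject per year", and SAP 2.2.2 repeats it as "Total number of EDs per patient per year". Both are rates.

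SAP 7.4.6 sits under the analysis of secondary endpoints. Its heading drops the time unit, and its text is "The total number of EDs on rFIXFc for each patient will be summarized", with a reference to 6.6.1.1. There the instruction is "The total number of EDs on rFIXFc for each patient will be summarized categorically", in bands from fewer than 5 to 100 or more, plus descriptive statistics, on the Safety Analysis Set. EDs accumulate from the first on-study injection and are not divided by time.

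The protocol's statistical section has the same gap. Section 16.2.3 annualizes bleeding episodes and consumption only, and the safety exposure summary in 16.5.2.3 reads "Duration of exposure and the total number of EDs to rFIXFc per subject will be summarized overall".

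The matching output in SAP Section 12 is "Summary of injections and days of exposure to rFIXFc by treatment regimen". Section 10 opens with "The major differences in the analysis described in this SAP compared to the protocol are" and gives three items, none about EDs.

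On when treatment ends, SAP 5.2.3 states "A patient who completes at least 50 EDs of rFIXFc and is not on an ITI regimen, is considered to have completed treatment".

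**The concern.** A count and a rate answer different questions. EDs per year describes how often a child is injected. Total EDs mixes that frequency with time on study, and the trial stops treating patients outside immune tolerance induction (ITI) once they have at least 50 EDs. Among completers the total therefore partly reflects the completion rule.

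If the SAP is programmed as written, one of seven secondary endpoints will be missing from the report and a different quantity will stand in its place. If someone then derives the rate after the data are in, the denominator will be chosen at that point, and the choice can move the answer.

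**Working it through.** **Is EDs per year derived anywhere?** The SAP's treatment of its per-year secondary endpoints compares as follows.

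- Bleeding rate (SAP 7.4.3): bleeds in the efficacy period / days in the efficacy period × 365.25. Annualized tables are listed in Section 12.
- Consumption (SAP 6.6.1.4 and 7.4.7): IU/kg in the efficacy period / days in the efficacy period × 365.25. An annualized table is listed.
- EDs (SAP 7.4.6 and 6.6.1.1): total count. No divisor, no 365.25, no annualized table title.

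Duration of dosing is summarized separately (SAP 6.6.1.2) but is not combined with EDs into a per-patient rate. Table shells are not among the documents, so only output titles could be checked. The plan states no figure for this endpoint, so there is nothing to reproduce.

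**How far can a total stand in for the rate?** Inputs: 50 EDs (completion rule) and participation of about 6 months to 3 years (Protocol 7.3).

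- Shortest: 50 / 0.5 = 100 EDs/yr.
- Longest: 50 / 3 = 16.7 EDs/yr.
- Weekly dosing, the recommended prophylactic start (Protocol 7.3.2): 365.25 / 7 = 52.2 EDs/yr.

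The same total is compatible with a six-fold range (100 / 16.7 = 6).

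**Does the denominator matter?** Assume 50 weekly doses, spanning 49 × 7 = 343 days.

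- All recorded: 50 / 343 × 365.25 = 53.2.
- Eight consecutive doses unrecorded, time from first to last dose as divisor: 42 / 343 × 365.25 = 44.7, about 16% below 53.2.
- Same data on the efficacy period: the 9 × 7 = 63-day gap exceeds 28 days and is removed under SAP 5.4.2.2, leaving 280 days. 42 / 280 × 365.25 = 54.8.

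**How does an efficacy-period rate behave in short exposures?** A patient who is only on prophylaxis is counted from first dose to last dose (SAP 5.3.1, 5.3.2), so the count exceeds the number of intervals by one. On weekly dosing, against 52.2:

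- 2 EDs in 7 days: 104.4 (+100%).
- 5 EDs in 28 days: 65.2 (+25%).
- 27 EDs in 182 days (26 weeks): 54.2 (+3.8%).
- 50 EDs in 343 days: 53.2 (+2.0%).

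These last figures describe the proposed rate, not the defect. They show why the 26-week subgroup is worth displaying.

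**Two small inconsistencies nearby.**

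- SAP 8 labels Cmax for incremental recovery as the 30-minute activity. The protocol schedules that sample at 10 (±5) minutes after the injection (4.2.1 footnotes, 9.1.4). Over the 20-minute difference, at the 66.49 h half-life for children under 6 years in Protocol Table 1, 1 − 2^(−(20/60)/66.49) = 0.35%. This assumes decline at the terminal rate throughout.
- In the all-injections response table of SAP 7.4.5, the second percentage divides injections by bleeding episodes. The categories then sum to 100% × rated injections per bleed. If 5% to 20% of bleeds had one further injection and every injection were rated (an assumption), the sum would be 105% to 120%. The first-injection table is sound and delivers the endpoint in Protocol 16.2.3.

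**The case against.** The strongest reply is that little is at stake. All these analyses are descriptive with no testing. Duration of dosing (6.6.1.2), dosing interval (6.6.1.3) and the exposure listing are already planned, so anyone can form the rate. The SAP also follows Protocol 16.5.2.3, and Section 10 claims to list only major differences.

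Much of this stands: no data are lost, and the primary endpoint does not depend on it. The rest does not close the gap. Section 16.5.2.3 is a safety exposure summary and does not replace the endpoint in 6.2.2. The dosing interval uses only consecutive prophylactic doses not separated by a bleed or major surgery, so it omits EDs for bleeds, surgery and episodic treatment. A rate formed later depends on choices the SAP has not made, as 44.7 against 54.8 shows.

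A reader might go further in two ways that the documents do not support.

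- That total EDs is simply fixed by the completion rule. Completion is at 50 or more EDs, treatment can end earlier through withdrawal or end of study, ITI patients follow another rule, and the planned bands run to 100 or more.
- That an endpoint worded as total EDs calls for whole dosing duration as the divisor. SAP 5.4.2 assigns the efficacy period to efficacy endpoints, 7.4.6 lies within the efficacy section, and 5.4.2.2 removes long prophylactic gaps because it attributes them to missing data. Keeping those days while the unrecorded EDs are absent would bias the rate downward.

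**Conclusion.** The point holds. The endpoint is defined as EDs per year in both documents, and the SAP's analysis of it yields total EDs, with no annualized table and no declared change. This is wrong as written rather than thin on detail, because following 7.4.6 exactly produces a different quantity.

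Its weight is minor to should-fix: one descriptive secondary endpoint out of seven, recoverable from planned data. The range of 100 to 17 EDs/yr shows how poorly a total identifies a rate. It should not be read as an expected error or as the spread the trial will see, because the participation time behind it includes screening and follow-up. The figures for weekly dosing and for unrecorded doses are illustrations under the stated assumptions.

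The Cmax label and the response percentage are real but small, and do not add to the severity.

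**What to change.** **Main change, SAP 7.4.6.** Add, for the Full Analysis Set, by regimen and overall:

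EDs per year = (EDs during the efficacy period / days in the efficacy period) × 365.25

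- Use the same denominator, evaluability rule (5.4.2), surgery and gap adjustments (5.4.2.1, 5.4.2.2) and 26-week subgroup (7.4.3) as for bleeding rate and consumption, where these apply. The evaluability rule already excludes a patient with a single prophylactic dose, whose duration would be zero.
- State whether a PK-dose day inside the efficacy period counts. The ED definition counts any dose, whereas consumption excludes PK amounts (6.6).
- Keep the total-ED summary in 6.6.1.1 as exposure data, and add the new table to Section 12.

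Downside: EDs in surgical periods are outside the rate, and short efficacy periods inflate it. The 26-week subgroup makes the inflation visible.

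**Consistency corrections.**

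- SAP 8: define Cmax as the 10 (±5)-minute sample that the protocol schedules.
- SAP 7.4.5: base the second percentage of the all-injections table on all injections given to treat bleeding. Keep bleeding episodes as the base for the first-injection table.

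Cost: SAP wording, one added table with one subgroup display, and shell edits. No new data are needed.

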**7.4.7. Total Annualized rFIXFc Consumption per Patient for the Prevention and Treatment of Bleeding Episodes**

Total annualized rFIXFc consumption per patient for the prevention and treatment of bleeding episodes will be summarized for the FAS using descriptive statistics. See Section 6.6.1.4 for details on the annualized rFIXFc consumption derivation.

This table will be presented by treatment regimen as described in Section 5.1.1.

**7.4.8. Number of Injections and Dose per Injection of rFIXFc Required to Resolve a Bleeding Episode**

The number of injections and average dose per injection (IU/kg) required to resolve a bleeding episode will be determined on both a per-bleeding episode and per-patient basis. For completeness, the total dose (IU/kg) administered to resolve a bleeding episode will also be determined on both a per-bleeding episode and per-patient basis. See Section 7.4.1 for details on the definition of a bleeding episode. A bleeding episode is considered resolved when treatment for the bleeding is no longer needed.

Per bleeding episode: The total number of injections will include the initial injection for a spontaneous bleed (SB), a traumatic bleed (TB), or a bleed of unknown type plus all injections identified as follow-up (FU) treatment for that bleed. For each bleed, the average dose per injection will be calculated as the average of all doses (IU/kg) administered among the SB/TB/Unknown and FU injections administered to treat that bleed; the total dose will be the sum of these doses. The number of injections required for the resolution of a bleeding episode will be summarized across all bleeding episodes both categorically (1, 2, 3, 4, >4; 1, >1; and ≤2, >2) and with descriptive statistics. The average dose per injection and total dose required for resolution of a bleeding episode will be summarized using descriptive statistics.

Per patient: The number of injections, average dose per injection, and total dose required to resolve each bleeding episode, as determined for the per-bleeding episode summaries, will be averaged across all bleeding episodes for each patient. The average number of injections required for resolution of a bleeding episode will be summarized both categorically (1 to <2, 2 to <3, 3 to <4, and ≥4; and 1 to <2, ≥2) and with descriptive statistics. The averages for the per-patient average dose per injection and total dose required for resolution of a bleeding episode will be summarized using descriptive statistics.

Bleeding episodes that were treated with non-study medication will be included in the determination of the number of injections required to resolve the bleeding episode but not in either the average dose per injection or total dose required.

For the above analysis, data from the FAS will be summarized. These tables will be presented by treatment regimen as described in Section 5.1.1.

**7.4.9. Response to Immune Tolerance Induction (ITI)**

Response to the ITI treatment regimen will be analyzed for the ITI Subgroup of the Full Analysis Set if the ITI Subgroup consists of at least 5 patients. Possible treatment responses are:

Success

[REDACTED]

- [REDACTED]
- [REDACTED]

[REDACTED]

- [REDACTED]
- [REDACTED]
- [REDACTED]

Failure:

ITI failure is defined as the inability to meet criteria for Success after 24 months on ITI.

Early Withdrawal/ITI Ongoing:

Patients may withdraw from the study during the ITI period before reaching 24 months or Success. In addition, any patients still in the ITI sub-study at the time of EOS will be included in this category.

Response categories of success, failure, early withdrawal, and ITI ongoing will be presented overall for the ITI Analysis Set, and separately for the inhibitor subgroups specified in Section 5.2.5, namely:

- Patients with high-titer inhibitors
- Patients with low-titer inhibitors that meet the clinically meaningful criteria

A data listing will be generated for all patients in the ITI sub-study. This will include date of first inhibitor sample with a positive result, all inhibitor and IR measurements after commencement of ITI therapy, as well as dosing information. It will also include elapsed time to each assessment and a flag to indicate the patient's ITI status.

## **7.5. Analysis of Exploratory Endpoint(s)**

### **7.5.1. Health Outcomes**

The health outcomes related to hemophilia in this study consist of the following items based upon the last month:

	Statistical Analysis Plan	Final v1.0
---	----------------------------------	-------------------

- How many times the child’s injection was administered by different persons
- Was work missed due to the child’s hemophilia
- Was school missed by the child due to his hemophilia
- Was the caregiver’s social/leisure time disrupted due to the child’s hemophilia
- Was household/domestic routine disrupted due to the child’s hemophilia

Full details of the questionnaire can be found in [Appendix A](#). The data will be summarized descriptively at each visit for the FAS.

### 7.5.2. Physicians Global Assessment of Response

Investigators record assessments of each patient’s response to their assigned rFIXFc regimen using the following 4 point scale:

- Excellent
- Effective
- Partially Effective
- Ineffective

The Investigators’ assessments will be summarized by visit for the FAS.

The number and percentage of patients in each response category will be tabulated. Percentages will be based on the number of patients for whom an assessment was provided at the respective visit. This table will also include a cumulative tabulation across all scheduled study visits; patients can be included in this tabulation up to all visits, once for each visit. Percentages for this collection of responses throughout the study will be based on the total number of assessments across all visits. In addition, these assessments will be provided in a data listing.

### 7.5.3. Surgery

Only data from major surgeries will be summarized for the surgery subgroup of the Full Analysis Set. All data will also be listed and similar listings will be written for data from minor surgeries.

Date of admission for surgery, start/end time for surgery, the surgical procedure performed, blood loss during and post operation, blood products used (including transfusion details for type of transfusion, date administered and amount given), date of discharge from hospital, date of last surgery follow-up and the Investigators’/Surgeons’ assessment of response to surgery measurements will be listed for all surgeries. Consumption on the day of surgery, including the number of injections required to maintain hemostasis, along with consumption and the number of injections administered over a 2-week period (Days 1-3, Days 4-14, and Days 1-14) following surgery will also be provided in a listing. The dosing intervals utilized during surgery will be characterized with the minimum and maximum intervals between injections required over this 2-week period.

	Statistical Analysis Plan	Final v1.0
---	----------------------------------	-------------------

